3.3.4.1 Withdrawal from trial treatment

An individual patient is to be withdrawn from trial treatment if:

- The patient wants to withdraw from trial treatment, without the need to justify the decision.
- The patient needs to take concomitant drugs that interfere with the investigational product or other trial medication. Please refer to Section 4.2.2 for restricted medication during this trial.
- The patient requires additional medical therapy or dose increase in patient's baseline medication, as deemed by the investigator, to treat the underlying UC due to disease worsening.
- The patient can no longer be treated with trial medication for other medical reasons such as surgery, AEs, other diseases, or pregnancy.
- The patient has repeatedly shown to be non-compliant with important trial procedures and, in the opinion of both, the investigator and sponsor representative, is not willing or able to stick to the trial requirements in the future.

Exclusion criteria occurring after randomization will not necessarily be a reason for withdrawal of a patient.

Given the patient's agreement, the patient will undergo the procedures for early treatment discontinuation and follow up as outlined in the Flow Chart and Section 6.2.3.

For all patients, the reason for withdrawal from treatment (e.g., adverse event) must be recorded in the eCRF. These data will be included in the trial database and reported.

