4.2 OTHER TREATMENTS, EMERGENCY PROCEDURES, RESTRICTIONS

4.2.1 Other treatments and emergency procedures

Patients in this trial are required to be on conventional, non-biologic treatment for UC.

Conventional treatment may consist of one or more of the following drugs (cf. Section 3.3.2, inclusion criteria), which are therefore permitted concomitant medications:

- Oral 5-ASA compound, with stable dose for at least 4 weeks prior to screening and throughout the trial
- 6-MP, MTX or AZA, with stable dose for at least 8 weeks prior to screening and throughout the trial
- Oral corticosteroids (≤ 20mg/day per day of prednisone or equivalent), with stable dose for at least 4 weeks prior to screening and throughout the trial. For equivalent doses of corticosteroids, please cf. Appendix 10.3.

Dose has to be stable throughout the trial. In the event that a patient experiences an intolerable increase of UC, as deemed by the investigator, during the course of the trial, the decision whether or not to discontinue treatment (if applicable) and start rescue treatment should be taken in the discretion of the investigator and in discussion with the CML. Rescue treatment may be any new medication or any increase in dose of a baseline medication.

Stable doses of concomitant therapies for chronic conditions, for which neither the condition nor the treatment are judged to exclude the patient from participation (cf. Section 3.3.3) are permissible. All concomitant medications should be carefully evaluated by the investigator, and the CML should be contacted when there are questions regarding concomitant medications.

Details of all concomitant medication will be recorded in the eCRF, along with the main reason for prescription. In addition, all prior treatment for UC within 12 months of Visit 1a will be recorded.

Infusion reactions including anaphylactic reactions:

In case of infusion reactions including anaphylactic reactions emerging during or after infusion of BI 655130, the investigator should consider in accordance with severity of the reaction and local standard of care to

- Immediately interrupt the infusion
- Treat with systemic anti-histamines and i.v. steroids and in case of a severe allergic reaction (eg, anaphylactic reaction) epinephrine

Also draw a plasma sample for IgE and ADA as detailed in the Lab Manual (Section 10 of the ISF).

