Based on patient's clinical course and medical judgment, the infusion may be re-initiated in case of mild or moderate infusion reactions (according to RCTC grading in Section 5 of the ISF) at lower speed with gradual increase to complete the infusion as detailed in the Instructions for Preparation and Handling of BI 655130 in the Investigator Site File.

In any case, the total duration of infusion should not exceed 240 minutes (4 hours) provided that the maximum time between the start of preparation and completion of administration of the solution to the patient does not exceed 300 minutes (5 hours).

In case of anaphylactic reaction, the investigator should discontinue treatment with BI 655130.

Cytokine release syndrome (CRS)

This syndrome manifests when a large number of immune cells becomes activated and releases inflammatory cytokines. It is clinically characterized by fever, chills, rigor and rash, possibly with nausea, dyspnoea, tachycardia and hypotension.

Potentially life-threatening complications of a cytokine release syndrome include cardiac dysfunction, respiratory distress syndrome, neurologic toxicity, renal and/or hepatic failure, and disseminated intravascular coagulation. In case of suspicion of a cytokine release syndrome, it is recommended to measure IL-6 levels in the local laboratory if the assay is available.

The investigator should discontinue treatment with BI 655130. Aggressive supportive care is essential for patients experiencing CRS, with early intervention for hypotension and treatment of concurrent infections. IL-6 receptor blockade with tocilizumab remains the mainstay pharmacologic therapy for CRS, though indications for administration vary among centres. Corticosteroids should be reserved for neurologic toxicities and CRS not responsive to tocilizumab (R16-5751).

0710598-04Trial ProtocolPage 35 of 82Proprietary confidential information © 2019 Boehringer Ingelheim International GmbH or one or more of its affiliated companies

Opportunistic infections or mycobacterium tuberculosis infections or serious infections

The investigator should discontinue treatment with BI 655130. Treatment of the infection has to be initiated according to local standard of care.

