4.2.2 Restrictions

Restrictions regarding previous and concomitant treatment are summarized in Table 4.2.2: 1.

Table 4.2.2: 1Restrictions regarding previous and concomitant treatment

Medication or class of medications	Restriction
Biologics	TNF inhibitors are only allowed in the past, if stopped for other reasons than primary non- response or lack of response
	Other biologics are excluded.
	Not allowed from 8 weeks prior to screening or 3 half-lives of agent from screening, whichever is longer, up to the end of the trial.
Cyclosporine, tacrolimus, mycophenolate mofetile and other immunomodulators not listed below	Not allowed from 8 weeks prior to screening or 5 half-lives of agent from screening, whichever is longer, up to end of the trial
AZA, 6-MP, MTX	Only allowed during the trial, if dose is stable for at least 8 weeks prior to screening and throughout the trial.
	For use of any of these drugs as concomitant medication, refer to Section $4.2.1$.

Trial Protocol

Page 36 of 82

Proprietary confidential information © 2019 Boehringer Ingelheim International GmbH or one or more of its affiliated companies

Table 4.2.2: 1Restrictions regarding previous and concomitant treatment (cont.)

	Restretions regarding previous and concommant treatment (cont.)
5-ASA	Oral administration:Only allowed during the trial, if dose is stable for at least 4 weeks prior to screening and throughout the trial.For use as concomitant medication, refer to Section 4.2.1.Rectal route of administration (5-ASA): Not allowed from 2 weeks prior to screening up to end of the trial
Corticosteroids	Oral administration: Only allowed at a dose of ≤ 20mg/day per day of prednisone or equivalent and with stable dose for at least 4 weeks prior to screening and throughout the trial. For use of oral corticosteroids as concomitant medication, refer to Section 4.2.1. Parenteral administration: Not allowed from 2 weeks prior to screening up to end of the trial Rectal administration: Not allowed from 2 weeks prior to screening up to end of the trial
NSAID Probiotics	Chronic use (Note: occasional use of NSAIDs and acetaminophen for headache, arthritis, myalgias, menstrual cramps, etc., and daily use of baby or low dose (81-162.5mg) aspirin for cardiovascular prophylaxis are permitted.) Not allowed from 2 weeks prior to screening up
110010405	to end of the trial
Antidiarrheals	Not allowed from screening up to end of the trial

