Categ Code		Description	Comments	Excluded from ¹	
D2		Prohibited medication use			
	D2.01	Use of restricted medication as per CTP Table 4.2.2: 1 on or after Screening or during the on-treatment period when not provided as a rescue treatment to stabilize a worsening disease condition- prior to or up to Week 12	If restricted medication is initiated during trial	CAS	#
		LABEL: Restricted medication prior to week 12			
	D2.02	Use of restricted medication as per CTP Table 4.2.2: 1 when not provided as a rescue treatment to stabilize a worsening disease condition – after Week 12	If restricted medication is initiated during trial	None	#
		LABEL: Restricted medication after week 12			
D3		Change in background medication			
	D3.01	Concurrent UC treatments need to be on stable doses during treatment:	Medical review	CAS	#
		Any dose change in background medication on or after Screening or during the on- treatment period unless it is due to rescue use or adverse event– prior to or up to Week 12			
		LABEL: Concurrent UC treatment not stable prior to Week 12			
	D3.02	Any dose change in background medication period unless it is due to rescue use or adverse event – after Week 12		None	#
		LABEL:			
		Concurrent UC treatment not stable after Week 12	Medical review		

Important protocol deviations (continued) Table 6.2: 1

PV will be detected manually

Source: BI reference document: "Identify and Manage Important Protocol Deviations (iPD)" [001-MCS-40-413] (2) ¹ See Section 6.3 for population definitions

TSAP for BI Trial No: 1368-0004 Page 23 of 48 Proprietary confidential information © 2019 Boehringer Ingelheim International GmbH or one or more of its affiliated companies

	egory /		~	-	
Cod	e	Description	Comments	Excluded from ¹	
Ε		Missing data None	Missing visits, evaluations, and tests will be considered missing data, not protocol deviations		
F		Study specific analysis			
F1		Other trial specific violation			
	F1.01	Incomplete diagnosis of ulcerative colitis	Medical review	CAS	#
		LABEL: Incomplete diagnosis of UC			
F2		Certain violations of procedures used to measure primary or secondary efficacy/biomarker data			
	F2.01	To be defined at the RPM, if applicable	Manual iPDs which have a potentially relevant effect on primary or secondary data	Any exclusion will be defined at the RPM/ DBLM/ MQRM.	#
G		Other safety related violations			
	G1	Pregnancy test not done for woman of child bearing potential		None	
		LABEL: Pregnancy test not done			

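### I.v. steroids that CTP 4.2.1 offers for an infusion reaction are barred by Table 4.2.2: 1, and SAP D2.01 as written then drops the treated completer from the main primary analysis set

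*Protocol*

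**What the plan says.** **CTP 4.2.1, infusion reactions.** For reactions during or after the infusion, "the investigator should consider in accordance with severity of the reaction and local standard of care to" take two steps. One is to interrupt the infusion. The other is "Treat with systemic anti-histamines and i.v. steroids and in case of a severe allergic reaction (eg, anaphylactic reaction) epinephrine". On clinical course and medical judgment, "the infusion may be re-initiated in case of mild or moderate infusion reactions". A further sentence reads "In case of anaphylactic reaction, the investigator should discontinue treatment with BI 655130".

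**CTP 4.2.2, Table 4.2.2: 1, corticosteroids.** "Parenteral administration: Not allowed from 2 weeks prior to screening up to end of the trial". No exception is printed on that line.

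**CTP 3.3.4.1.** One reason for withdrawal from trial treatment is "The patient needs to take concomitant drugs that interfere with the investigational product or other trial medication", with a pointer to Section 4.2.2 for restricted medication.

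**SAP 6.2, Table 6.2: 1.** D2.01 covers use of a Table 4.2.2: 1 medication from screening onwards. It limits this to use "when not provided as a rescue treatment to stabilize a worsening disease condition", and to the time up to and including Week 12. Its consequence is exclusion from the CAS. D3.01, on dose changes in background medication, exempts changes due to rescue or to an adverse event.

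**SAP 6.3, 6.6.2 and 6.6.6.** The CAS is the main set for the primary endpoint. The observed-cases rule sets values after rescue medication to missing and applies to the RNA data. Rescue is whatever the investigator ticks as such in the CRF.

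**The concern.** Infusion reaction is an adverse event of special interest in this trial, so the protocol expects that one may occur. It names a treatment for it in one section and bars that treatment in the next. A site that gives i.v. steroids as 4.2.1 contemplates records prohibited-medication use, and the SAP makes that a reason to leave the CAS.

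Two things are at stake. First, the primary analysis would lose a patient who finished treatment, including biopsies taken before any steroid was given. The loss would be triggered by a reaction to the study drug, so the set would be selected on a drug effect. Second, the two analysis sets would treat the same event in opposite ways: the CAS discards unaffected samples, while the FAS keeps samples taken after the steroid unless a CRF box happens to be ticked.

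**Working it through.** No figure in the plan is at issue; the sample size of 10 rests on feasibility (CTP 7.7). The check is of text against text, with some arithmetic for scale.

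**1. Is there an exception or an order of precedence?** None is stated. Table 4.2.2: 1 does carry links and exceptions elsewhere: the oral corticosteroid entry refers to 4.2.1, and the NSAID entry allows occasional use. The parenteral line has neither. According to the amendment log, amendment 1 added the infusion-reaction guidance to 4.2.1, and its listed change to 4.2.2 concerned biologics. That is a plausible origin of the gap, not proof of one.

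**2. Does D2.01 apply at every infusion?** Infusions are on Days 1, 29 and 57, and Week 12 is Day 85. All three come earlier, so a steroid given for a reaction falls under D2.01 (CAS exclusion) and not D2.02 (after Week 12, no exclusion).

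**3. Does an exemption apply?** D2.01 exempts use only as rescue to stabilise worsening disease. An infusion reaction is not that. The adverse-event exemption in D3.01 is missing from D2.01.

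**4. Who is affected?**
- Anaphylaxis: 4.2.1 says to discontinue. The patient is then not a completer and is outside the CAS whatever D2.01 says. Replacement is possible for withdrawal before Week 12 (CTP 7.7, up to 4).
- Mild or moderate reaction, i.v. steroid given, treatment completed: D2.01 alone removes the patient. CTP 7.7 covers early withdrawal from treatment only, so no replacement follows.

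**5. What would be saved by censoring instead of excluding?** The post-baseline time points are V2 (4 h), V3 (Day 4), V4 (Week 2), V7 (Week 8) and EoT (Week 12) (SAP 7.4). V7 biopsies are taken before dosing (CTP 6.2.2). The pre-baseline V1b biopsy is not counted, because the primary model uses only the last pre-dose value (CTP 7.3.1).

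| Steroid given at | Post-baseline biopsies before the steroid | After it |
|---|---|---|
| Day 1, before the 4 h biopsy | 0 of 5 | 5 |
| Day 1, after the 4 h biopsy | 1 of 5 (4 h) | 4 |
| Week 4 | 3 of 5 (4 h, Day 4, Week 2) | 2 |
| Week 8 | 4 of 5 (4 h, Day 4, Week 2, pre-dose Week 8) | 1 |

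**6. Scale.** One patient is 1/10 = 10% of the planned number. As a rough guide, standard errors grow by √(10/(10 − k)) when k patients leave: √(10/9) = 1.054 for one (about 5%) and √(10/8) = 1.118 for two (about 12%).

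The documents give no rate of steroid-treated reactions in UC. With an assumed per-patient rate p, the chance that at least one of 10 patients is affected is 1 − (1 − p)^10:

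| Assumed p | Chance of at least one |
|---|---|
| 1% | 9.6% |
| 5% | 40.1% |
| 10% | 65.1% |
| 20% | 89.3% |

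**The case against.** The other side has several sound arguments.

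- **The guidance is discretionary.** A reader might infer that the protocol orders i.v. steroids and that a site therefore cannot obey both sections. The documents do not support that. The step is to be considered according to severity and local practice, and a site that considers steroids without giving them breaches neither section. Section 4.2.1 can also be read as a specific emergency provision beside a general table, and CTP 8 leaves standard medical care with the treating physician. This stands, and it limits the conflict to the point at which the steroid is given. The reading of 4.2.1 as prevailing is nowhere stated.
- **Withdrawal does not follow automatically.** A reader might infer that such a patient must come off treatment under 3.3.4.1. That rule depends on the drug interfering with the trial medication, and nothing says that i.v. steroids for a reaction do so. This stands; what remains is that the pointer to 4.2.2 leaves the question open.
- **The exclusion is reviewed and is not total.** Each deviation is assessed for importance (SAP 6.2), and set allocation is decided at the latest at the report planning or database lock meeting (SAP 6.3). D2.01 does not remove the patient from the FAS, to which the secondary efficacy endpoints are assigned in Table 6.3: 1. This stands in part. Review case by case is late in an open-label trial, and the FAS analysis of the primary endpoint is among those that may be conducted.
- **The event may not happen.** CTP 2.3 says that no infusion reactions were reported in phase I. This stands; the point rests on unreconciled text and not on frequency.
- **Censoring may recover little.** This is true for a Day 1 reaction treated early, as the timing table shows.

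**Conclusion.** The inconsistency is real but bounded. Two protocol passages are not reconciled for i.v. steroids given for an infusion reaction, and D2.01 read literally excludes a completer treated as 4.2.1 contemplates. The effect is confined to patients who receive the steroid, continue and complete. For each, the main primary analysis loses 1 of 10 planned patients without replacement, with between 0 and 4 of 5 post-baseline biopsies that preceded the steroid. In the FAS, post-steroid values remain unless rescue is ticked, so the handling depends on how the site labels the event.

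This assumes that D2.01 is applied as printed and that the patient otherwise qualifies for the CAS. The chance of its happening cannot be derived from the documents. It is worth correcting because the remedy is small and the event is one that the protocol itself anticipates.

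**What to change.** **Protocol.** The sponsor must reconcile the infusion-reaction text in CTP 4.2.1 with the parenteral corticosteroid line of Table 4.2.2: 1, and clarify whether 3.3.4.1 applies. No view is taken on which clinical rule is right.

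**SAP.** Align D2.01 with the reconciled text. Where the protocol allows medication given for an infusion reaction, list it but do not exclude the patient from the CAS for it. Set values after the systemic steroid to missing in both CAS and FAS, as the observed-cases rule in SAP 6.6.2 already does after rescue. Trigger this from the recorded medication and its reason, not from the rescue tick. If the reconciled protocol does not allow the medication, D2.01 can stay, but the SAP should say that this case is covered.

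**Cost.** A cross-reference in the protocol sections concerned, one exception in D2.01 and one added censoring trigger in SAP 6.6.2. The downside is small: the CAS may hold a patient with few or no usable later samples, so the number of patients contributing at each time point should be shown.

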4.2.2 Restrictions

Restrictions regarding previous and concomitant treatment are summarized in Table 4.2.2: 1.

Table 4.2.2: 1Restrictions regarding previous and concomitant treatment

Medication or class of medications	Restriction
Biologics	TNF inhibitors are only allowed in the past, if stopped for other reasons than primary non- response or lack of response
	Other biologics are excluded.
	Not allowed from 8 weeks prior to screening or 3 half-lives of agent from screening, whichever is longer, up to the end of the trial.
Cyclosporine, tacrolimus, mycophenolate mofetile and other immunomodulators not listed below	Not allowed from 8 weeks prior to screening or 5 half-lives of agent from screening, whichever is longer, up to end of the trial
AZA, 6-MP, MTX	Only allowed during the trial, if dose is stable for at least 8 weeks prior to screening and throughout the trial.
	For use of any of these drugs as concomitant medication, refer to Section $4.2.1$.

Trial Protocol

Page 36 of 82

Proprietary confidential information © 2019 Boehringer Ingelheim International GmbH or one or more of its affiliated companies

Table 4.2.2: 1Restrictions regarding previous and concomitant treatment (cont.)

	Restretions regarding previous and concommant treatment (cont.)
5-ASA	Oral administration:Only allowed during the trial, if dose is stable for at least 4 weeks prior to screening and throughout the trial.For use as concomitant medication, refer to Section 4.2.1.Rectal route of administration (5-ASA): Not allowed from 2 weeks prior to screening up to end of the trial
Corticosteroids	Oral administration: Only allowed at a dose of ≤ 20mg/day per day of prednisone or equivalent and with stable dose for at least 4 weeks prior to screening and throughout the trial. For use of oral corticosteroids as concomitant medication, refer to Section 4.2.1. Parenteral administration: Not allowed from 2 weeks prior to screening up to end of the trial Rectal administration: Not allowed from 2 weeks prior to screening up to end of the trial
NSAID Probiotics	Chronic use (Note: occasional use of NSAIDs and acetaminophen for headache, arthritis, myalgias, menstrual cramps, etc., and daily use of baby or low dose (81-162.5mg) aspirin for cardiovascular prophylaxis are permitted.) Not allowed from 2 weeks prior to screening up
110010405	to end of the trial
Antidiarrheals	Not allowed from screening up to end of the trial
Life-attenuated vaccin	nes Not allowed from 6 weeks prior to screening up to end of the trial
Antibiotics for IBD	Not allowed from 4 weeks prior to screening up to end of the trial

4.2.2.1 Restrictions on diet and life style

Patient should be fasted for at least 8 hours prior to collection of the safety laboratory samples, starting from Visit 2 and as indicated in the Flow Chart.

4.2.2.2 Restrictions regarding women of childbearing potential

Women of childbearing potential must use the contraception methods as described in the patient information.

4.3 TREATMENT COMPLIANCE

Compliance will be assured by administration of all trial medication in the study centre by the authorised personnel (e.g., study nurse). The measured plasma concentration will provide additional confirmation of compliance.

Subjects who are not compliant (e.g., who do not appear for scheduled visits or violate trial restrictions) may be removed from the trial and the eCRF will be completed accordingly (for further procedures, please see Section 3.3.4.1).

Any missed dose has to be documented and reported to the CML.

Page 38 of 82 Proprietary confidential information © 2019 Boehringer Ingelheim International GmbH or one or more of its affiliated companies

5. VARIABLES AND THEIR ASSESSMENT

5.1 **TRIAL ENDPOINTS**

5.1.1 **Primary Endpoint**

The total number of deregulated genes comparing baseline to post-treatment, analysed by gene expression of mucosal biopsies via RNA sequencing (RNAseq), per time point up to week 12.

The total number of deregulated genes per time point will be reported. Further details on the planned analyses will be given in Section 7.3.

5.1.2 **Secondary Endpoints**

- Drug related AEs •
- Percent change in CRP from baseline to Week 12 •
- Percent change in faecal calprotectin from baseline to Week 12 •
- Percent change in faecal lactoferrin from baseline to Week 12 •
- Clinical remission at Week 12 based on Mayo Score (Mayo Score ≤2 with all . subscores ≤ 1)

For a definition of (modified) Mayo Score refer to Appendix 10.1

please

Page 39 of 82

Proprietary confidential information © 2019 Boehringer Ingelheim International GmbH or one or more of its affiliated companies

